## 9.2 Endpoints

Please refer to trial protocol synopsis ([see section 1.5](#)).

## 9.3 Sample Size Calculation

### Primary objective

The primary objective of the trial is to demonstrate equivalence of three consecutively produced lots of IMVAMUNE® in terms of humoral immunogenicity in vaccinia-naïve subjects after two doses. Assuming a significance level of 5%, an analyzable sample size of 600 in each group for the per protocol set, and an expected log10 titer SD of 0.85 in all groups for the PRNT, then the primary hypothesis of the GMT based on the PRNT at Visit 4 (i.e. after two IMVAMUNE® vaccinations) has a power of >80% of showing equivalence for all three IMVAMUNE® groups, using an equivalence margin of  $\Delta=0.301$  on the log10 scale.

In order to account for a dropout rate of about 15%, which has been observed in previous IMVAMUNE® trials, blood will be analyzed from a total of 700 subjects in each group.

In order to allow a proper safety analysis as described in the sections below, 300 additional subjects will be enrolled in each group to ensure that a total of 1,000 subjects per group are available.

### Secondary objectives

A safety sample size of 1,000 in each of the three IMVAMUNE® groups will give a combined IMVAMUNE® safety population of 3,000 subjects. With this sample size the trial will have a 95% chance of detecting any uncommon AEs, i.e. with an incidence of at least 1/1,000.

An important cardiac safety objective of this trial is to demonstrate that the incidence of myo-/pericarditis cases in the combined IMVAMUNE® trial groups (Groups 1–3) is less than 1/330 (lower 95% confidence limit of the 10 cases out of 1,675 subjects observed in the ACAM2000® development program). If no cases of myo-/pericarditis are observed in the 3,000 IMVAMUNE® subjects then the true incidence of myo-/pericarditis will be significantly ( $\alpha=0.05$ ) below the 1/1,000 rate. In contrast, if one or two cases of myo-/pericarditis are observed in the three combined IMVAMUNE® trial groups then the observed rate is significantly below 1/330 ( $\alpha=0.05$ ), which is the most optimistic rate that is likely for the incidence of ACAM2000®.

It is also relevant to compare the observed incidence of myo-/pericarditis cases in the combined IMVAMUNE® trial groups to that seen in the placebo group (Group 4). Hence cardiac monitoring will be performed in all 1,000 subjects of every trial group (including the placebo group) two weeks after each IMVAMUNE® / placebo administration.

The background incidence of myo-/pericarditis from literature is assumed to be 1–5 cases per 100,000 in the healthy population ([Karjalainen and Heikkilä, 1999](#)), which represents the incidence expected following vaccination with IMVAMUNE®. If we assume that the background rate of the healthy population is at the upper range of this estimate, i.e. 0.00005 (5/100,000), then the chance of observing a single case of myo-/pericarditis in the combined IMVAMUNE® groups is 13.9%. Therefore, the observation of a single case of myo-/pericarditis would not be a significant event. The observation of 2 or more cases of myo-

/pericarditis would occur with a probability of only 1.02%, and hence would be an unlikely event.

In summary, if no case of myo-/pericarditis would be observed in the placebo group and no cases in the 3,000 subjects of the combined IMVAMUNE® trial groups then it can be concluded that the incidence is statistically significantly lower than 1/1,000. Alternatively, if a single case would be observed in the combined IMVAMUNE® trial groups then the rate is still statistically significantly lower than 1/330 (which is the best case scenario for ACAM2000®), and is not significantly different from the assumed background incidence rate of 5/100,000. Finally, if two cases would be observed then this is still significantly lower than 1/330, but is significantly higher than the background incidence of 5/100,000.

However, the chance of observing a single case of myo-/pericarditis in the 1,000 placebo subjects is only 4.9% (assuming the background rate is 0.00005, Karjalainen and Heikkilä, 1999). Hence the observation of a single case of myo-/pericarditis in the placebo group would be significant evidence that the baseline rate in the healthy trial population is actually higher than 0.00005.

Careful cardiac monitoring of all subjects will also allow comparison between groups with regard to the incidence of other cardiac events such as ECG changes, which are expected to be observed in all trial groups, including placebo subjects. A completed Phase II IMVAMUNE® trial enrolling 745 subjects included close cardiac monitoring and revealed several cases of changes in cardiac status in a young, healthy population. Most of these cardiac observations were assessed to be clinically not significant and similarly distributed amongst all trial groups including the placebo group. These data demonstrate the necessity to include a placebo arm for filtering out background pathology in healthy subjects not receiving IMVAMUNE®.

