### 2.3 Second Generation Smallpox Vaccines

Second generation smallpox vaccines are derived from first generation VV strains by plaque purification and manufactured in cell cultures according to modern Good Manufacturing Practice (GMP) standards. Vaccination of individuals with these vaccines is performed in the same way as with first generation smallpox vaccines, namely by intradermal administration (scarification) of a single dose.

ACAM2000® developed by Acambis Inc. is based on the Dryvax® NYCBH strain. In preparation of a Biologics License Application at the US Food and Drug Administration (FDA), Acambis conducted two pivotal Phase III clinical trials enrolling either vaccinia-naïve or vaccinia-experienced populations. The trials were designed to compare the safety, tolerability and efficacy of ACAM2000® with Dryvax®. In total, the ratio of individuals in these trials receiving ACAM2000® and Dryvax® was 3:1. Results were publicly made available in May 2007 ([ACAM2000 VRBPAC Briefing Document, 2007](#)).

Safety information available from these trials suggests that the non-serious adverse reactions were typical for vaccines administered by injection or scarification. The majority (99% and 97% respectively) of subjects experienced at least one treatment-emergent AE after vaccination. The AEs most commonly reported fell into four distinct categories: reactions at the vaccination site, lymphadenitis, constitutional “flu-like” symptoms and minor gastrointestinal symptoms. Of special interest, however, were a total of 10 serious cases of myo-/pericarditis that were reported within the ACAM2000® development program. In a total vaccinia-naïve population of 1,675 subjects, these events occurred in seven subjects treated with ACAM2000® (5.73 events per thousand vaccinations) and in three subjects having received Dryvax® (10.38 events per thousand vaccinations for a combined calculated incidence of 5.97 cases of myo-/pericarditis per thousand vaccinations - 95% confidence interval of 2.87 to 10.95 cases per thousand). These figures represent quite a high rate of potentially life-threatening serious AE following vaccination with a prophylactic vaccine.

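### The 1/330 myo-/pericarditis benchmark disagrees with the lower limit in section 2.3 and is a pooled ACAM2000 and Dryvax figure labelled as the best case for ACAM2000

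*Protocol*

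**What the plan says.** Section 2.3 describes 10 serious myo-/pericarditis cases in the ACAM2000 development programme. On the denominator and the split it says: "In a total vaccinia-naïve population of 1,675 subjects, these events occurred in seven subjects treated with" ACAM2000, at "5.73 events per thousand vaccinations) and in three subjects having received" Dryvax, the latter at "10.38 events per thousand vaccinations for a combined calculated incidence of 5.97 cases" per thousand. The pooled result is a "combined calculated incidence of 5.97 cases of myo-/pericarditis per thousand vaccinations - 95% confidence interval of 2.87 to 10.95 cases per thousand".

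Section 9.3 (Secondary objectives) takes the same 10/1,675 and states the aim of showing that the incidence in the combined IMVAMUNE groups "is less than 1/330 (lower 95% confidence limit of the 10 cases out of 1,675 subjects observed in the" ACAM2000 programme. It describes 1/330 as the rate "which is the most optimistic rate that is likely for the incidence of" ACAM2000, and its summary repeats the idea: "which is the best case scenario for" ACAM2000.

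Three conclusions are stated in advance for 3,000 IMVAMUNE subjects at alpha = 0.05, with no sidedness given. Zero cases would be significantly below 1/1,000. One case would be significantly below 1/330, and so would two.

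**The concern.** One dataset carries two lower 95% limits in the same protocol, and a reader cannot tell which is the intended benchmark. Separately, a limit computed from ACAM2000 and Dryvax recipients together is presented as a bound for ACAM2000 alone. Dryvax has the higher stated rate (10.38 against 5.73 per thousand), so pooling raises the supposed best case.

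Both faults point the same way, because a higher benchmark is easier to fall below. At stake is a comparative safety statement against a named licensed vaccine, under what section 9.3 calls an important cardiac safety objective.

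**Working it through.** **Inputs.** Section 2.3: 10 cases in 1,675 subjects; 7 ACAM2000 cases at 5.73 per thousand; 3 Dryvax cases at 10.38 per thousand; a 3:1 ratio of ACAM2000 to Dryvax recipients across the two Phase III trials. Section 9.3: benchmark 1/330, N = 3,000, alpha = 0.05.

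**1. The two stated limits.** 1,000/330 = 3.03 per thousand. 1,000/2.87 = 348, so section 2.3 gives 1/348.

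**2. Reproducing them from 10/1,675 (two-sided 95%).**
- Exact (Clopper-Pearson), lower limit = 2.5% quantile of Beta(10, 1,666): 2.867 per thousand (1/348.9), upper limit 10.952. This is the section 2.3 interval.
- Mid-P lower limit: 3.036 per thousand (1/329.3). Continuity-corrected Wilson gives 3.037 (also 1/329.3).
- For comparison: Jeffreys 1/325, Agresti-Coull 1/324, Wilson 1/308, Wald 1/438.

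So 1/330 is a possible 95% lower limit, but not by the method behind section 2.3.

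**3. Denominators.** 7/0.00573 = 1,222 and 3/0.01038 = 289, which sum to 1,511, not 1,675. The pooled 5.97 per thousand needs 1,675 (10/1,675 = 5.97; 10/1,511 = 6.62). The arm rates and the pooled rate therefore do not share one denominator.

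**4. ACAM2000 alone.** The denominator is an assumption: 1,222 from the stated rate, or 1,675 × 3/4 = 1,256 from the 3:1 ratio.
- Exact lower limit for 7/1,222: 2.31 per thousand (1/434). For 7/1,256: 2.24 per thousand (1/446).
- Mid-P lower limit: 2.51 (1/399) and 2.44 (1/410) respectively.

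All four are stricter than 1/330.

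**5. Sidedness.** For zero cases against 1/1,000, P = (1 − 0.001)^3000 = 0.0497. This is significant at 0.05 only one-sided; the two-sided 95% upper limit for 0/3,000 is 1.23 per thousand. The protocol's own statement therefore implies one-sided 0.05.

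**6. The stated one- and two-case conclusions.** One-sided exact P = P(X ≤ k) for X ~ Binomial(3,000, benchmark):

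| Benchmark | 1 case | 2 cases |
|---|---|---|
| 1/330 (section 9.3) | 0.0011 | 0.0057 |
| 1/348 (section 2.3) | 0.0017 | 0.0084 |
| 1/434 to 1/446 (ACAM2000 only, exact) | 0.008 to 0.009 | 0.031 to 0.036 |

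Exact two-sided 95% upper limits in 3,000 are 1.86 per thousand for one case and 2.41 for two. Both lie below 2.87. The two-case limit lies above the ACAM2000-only exact limits of 2.31 and 2.24; the one-case limit lies below them.

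**The case against.** The best defence is that 1/330 is not an arithmetic error. It is a legitimate lower limit by mid-P or continuity-corrected Wilson, and moving to 1/348 alters none of the conclusions for zero, one or two cases, one-sided or two-sided. Under the one-sided 0.05 that the protocol implies, two cases remain significant even against the ACAM2000-only exact limit. With mid-P applied to ACAM2000 alone (2.51 to 2.44 per thousand), two cases also hold two-sided, since 2.41 lies below both values. The ACAM2000 denominator is itself uncertain. All of this stands, and it limits the consequence. It does not remove the disagreement between sections 2.3 and 9.3, and no choice of interval method makes a pooled limit an ACAM2000 limit.

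Three stronger readings are tempting but unsupported:
- A reader might infer that a stated verdict flips at three cases, where the two-sided upper limit of 2.92 per thousand falls between 2.87 and 3.03. Section 9.3 draws no conclusion for three cases, and at one-sided 0.05 three cases pass against both 1/330 (P = 0.020) and 1/348 (P = 0.028).
- A reader might shrink 3,000 by the 15% dropout rate. Section 9.3 applies that rate to the PRNT sample (700 to reach 600). The safety set in section 9.4 needs only one dose and post-vaccination safety data.
- A reader might take 1/330 for a formal success criterion. No endpoint in the synopsis tests against it, the synopsis objective compares with placebo, and section 9.5 treats tests of secondary endpoints as descriptive.

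**Conclusion.** The point holds as an inconsistency and a mislabelling. The benchmark of 3.03 per thousand should read 2.87 if it is to agree with section 2.3, about 5% lower, and it describes ACAM2000 and Dryvax combined. An ACAM2000-only exact limit would be roughly a quarter lower than the stated benchmark (2.31 to 2.24 against 3.03), on the assumption of 1,222 to 1,256 recipients.

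Only one stated conclusion is sensitive. The two-case statement, read as a claim about ACAM2000, fails if the limit is exact and the test is two-sided at 0.05. It holds at one-sided 0.05.

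The sample size and the primary lot-consistency analysis are unaffected. Severity is minor to moderate.

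**What to change.** - Use one lower limit in sections 2.3 and 9.3 and name the method. The simplest choice is 2.87 per thousand (1/348, exact), labelled as ACAM2000 and Dryvax combined, with the best-case wording for ACAM2000 removed.
- If the claim is meant for ACAM2000 alone, use that vaccine's own lower limit once its denominator is settled.
- Reconcile the arm rates in section 2.3 (implying 1,222 + 289 = 1,511) with the total of 1,675.
- State that alpha = 0.05 is one-sided, as the zero-case statement implies.
- Restate the one- and two-case conclusions against the chosen limit.

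The cost is protocol wording, carried into the statistical analysis plan if it repeats the benchmark, and a slightly less favourable figure. No additional subjects are needed.

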## 1.6 Trial Procedure Schedule

Visit (V)	SCR	V1	V2	V3	V4	V5	FU Phone
Day / Visit +... D	-28- -1	0	V1 +12-16	V1 +28-35	V3 +12-16	V3 +28-35	V3 +182-210
Target week	- 4	0	2	4	6	8	30
Procedures							
Informed consent	X						
Check incl. / excl. criteria	X	X					
Check withdrawal criteria				X			
Medical History	X						
Assessment for previous smallpox vaccination including check for a scar	X						
Complete physical exam	X						
Evaluation of vital signs	X	X	X	X	X	X	(X) 
Calculate individual cardiac risk factor	X						
Evaluation of family cardiac risk factors	X						
Recording of baseline signs and symptoms	X	X					
Targeted physical exam incl. auscultation of the heart and lung		X	X	X	X	X	(X) 
ECG 	X		X		(X) 		
Recording of prior and concomitant medication	X	X	X	X	X	X	
Counseling on avoidance of pregnancy for WOCBP 	X	X		X			
AE/SAE/AESI recording		X	X	X	X	X	X 
Lab							
Pregnancy test for WOCBP 	X	X		X		X	
Obtaining blood for safety lab 	X		X		X		(X) 
Total, HDL and LDL cholesterol	X						
Troponin I testing 	X		X		(X) 		
Sera collection for antibody analysis		X			X		
Vaccination							
Vaccine administration & Subject observation (≥ 30 minutes)		X		X			
Recording of immediate AEs		X		X			
Handout of memory aid		X		X			
Collection of memory aid			X		X		
Examination of injection site			X		X		
Blood volume							
Appr. blood volume drawn (ml) 	11	8	11	0	19	0	(11) 
Cumulative blood volume drawn (ml) 	11	19	30	30	49	49	(60) 

 If at the telephone FU a serious condition is detected, the trial subject will be requested to return to the CTS and the respective examinations will be performed.

 Only if clinically indicated, i.e. in the presence of cardiac signs or symptoms.

 New SAEs/AESIs and changes to SAEs/AESIs/AEs ongoing at V5 only.

 At SCR, a serum test must be performed. At other visits, a urine pregnancy test will be performed.

 If clinically indicated, additional safety measures can be taken at any other trial visits or at unscheduled visits.

 Approximate amounts of single blood draws: Safety lab including all tests: 11 ml; antibody analysis: 8 ml.

 Review of acceptable contraceptive methods and recent menstrual history with WOCBP.

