**Visit 2 (Visit 1 + 12–16 days)**

**The following tasks will be performed:**

- Targeted physical examination including auscultation of the heart and lungs
- Evaluation of vital signs
- Examination of the injection site
- Performing ECG
- Collection of the memory aid handed out at Visit 1, review with subject
- Blood draw for safety laboratory ( 11 ml) including troponin I
- Recording of AEs/SAEs/AESI and concomitant medication

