**Visit 4 (Visit 3 + 12–16 days)**

**The following tasks will be performed:**

- Targeted physical examination including auscultation of the heart and lungs
- Evaluation of vital signs
- Examination of the injection site
- Perform ECG (if clinically indicated)
- Blood draw for safety laboratory (11 ml, including troponin I testing if clinically indicated)
- Blood draw (serum collection, 8 ml) for antibody analysis
- Recording of AEs/SAEs/AESIs and concomitant medications
- Collection of the Memory aid handed out at Visit 3, review with subject

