### ECG

A standard 12-lead ECG will be taken at SCR and at Visit 2. At Visit 4 an ECG is only done

if clinically indicated. ECGs will be evaluated by central ECG reading. The workflow and communication flow will be provided in a separate manual.

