#### Troponin I

Troponin I will be measured at the SCR and at Visit 2. At Visit 4 troponin I measurement is only done if clinically indicated.

[figure not shown]
Cardiac events fulfill the definition of an AESI as described under [section 8.1.3.3](#). The investigator will be asked to assess the clinical significance of the case.

Case definitions as published by the Centers of Disease Control and Prevention ("Update: Cardiac-Related Events During the Civilian Smallpox Vaccination Program --- United States, MMWR May 30, 2003, Vol. 52, No. 21, p. 494") are provided in [Appendix II](#) in order to:

- help investigators to recognize possible events of acute myocarditis and/or pericarditis and
- distinguish from unspecific and isolated ECG changes without or with unclear clinical significance.

Subjects who develop any kind of cardiac signs or symptoms during the trial such as but not limited to chest pain, dyspnea, arrhythmia or edema are referred to a local cardiologist for cardiac evaluation such as (treadmill) ECG, cardiac enzymes and/or echocardiogram. Depending on the results of these evaluations, further diagnostic tests will be done as recommended by the cardiologist and subjects will be followed up at a frequency determined by the cardiologist. AESIs will be followed up until complete resolution or until the sequelae are stable and considered to be permanent.

[Figure 1](#) outlines the algorithm for assessment of cardiac events.

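### Section 9.3 describes cardiac monitoring of everyone after both doses, but the schedule gives every subject an ECG and troponin I only after the first

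*Protocol*

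**What the plan says.** Section 9.3 (Secondary objectives) turns to the comparison of the pooled vaccine groups with placebo and concludes: "Hence cardiac monitoring will be performed in all 1,000 subjects of every trial group (including the placebo group) two weeks after each" IMVAMUNE or placebo administration. Two weeks after each dose means Visit 2 (Visit 1 plus 12 to 16 days) and Visit 4 (Visit 3 plus 12 to 16 days). The section then adds: "Careful cardiac monitoring of all subjects will also allow comparison between groups with regard to the incidence of other cardiac events such as ECG changes".

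The operational sections describe something narrower:

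- The schedule in section 1.6 marks ECG and troponin I without condition at screening and Visit 2. At Visit 4 both entries are in brackets, with footnote 2: "Only if clinically indicated, i.e. in the presence of cardiac signs or symptoms".
- The task lists in section 4.2.2 have "Performing ECG" at Visit 2 and "Perform ECG (if clinically indicated") at Visit 4.
- Section 8.2.7 says of ECG "At Visit 4 an ECG is only done" when clinically indicated, and of troponin "At Visit 4 troponin I measurement is only done if clinically indicated".
- Section 8.2.8 makes troponin I mandatory only at screening and Visit 2.

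**The concern.** The statistical section credits the trial with a surveillance property that its schedule does not deliver. A reader of section 9.3 alone would take it that every subject in all four groups has an equivalent cardiac work-up two weeks after both doses, and that group differences in ECG findings can be read as randomised comparisons across the whole vaccination course.

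What is at stake is mainly silent findings. Section 8.1.3.3 defines an adverse event of special interest by any one of three routes: a cardiac sign or symptom, a clinically significant ECG change, or troponin I at or above twice the upper limit of normal. The last two need no symptom. After dose 2 they come to light only if something else has prompted the test. The question is a live one for this product: section 2.6.1 lists increased troponin I among the common suspected reactions (at least 1% and below 10%), although it does not say how many of those rises reached twice the upper limit.

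**Working it through.** **1. The passages side by side**

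| Assessment | Two weeks after dose 1 (Visit 2) | Two weeks after dose 2 (Visit 4) |
|---|---|---|
| ECG | all subjects (1.6, 4.2.2, 8.2.7) | only if clinically indicated (1.6, 4.2.2, 8.2.7) |
| Troponin I | all subjects (1.6, 4.2.2, 8.2.7, 8.2.8) | only if clinically indicated (same sections) |
| Heart and lung auscultation, vital signs, AE/AESI recording | all attending | all attending |
| Section 9.3 | all subjects monitored | all subjects monitored |

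The last row matches the first two rows at Visit 2 but not at Visit 4.

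**2. Size**

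Planned two-week post-dose time points: 4 groups × 1,000 subjects × 2 doses = 8,000. With a scheduled ECG and troponin I: 4 × 1,000 × 1 = 4,000, all after dose 1. For the vaccine groups alone the figures are 6,000 and 3,000. Per subject, everyone who attends Visit 2 has one universal post-vaccination ECG and troponin I instead of two. These are planned numbers; subjects who do not receive dose 2 have no Visit 4 at all (section 4.2.5).

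**3. Which outcomes depend on the missing tests**

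- *Asymptomatic ECG or troponin AESIs (8.1.3.3):* sought in everyone after dose 1, not after dose 2.
- *Possible or probable myocarditis (Appendix II):* requires dyspnea, palpitations or chest pain. Those symptoms are the trigger for Visit 4 testing and lead to cardiology referral (8.2.7).
- *Possible or probable pericarditis (Appendix II):* requires chest pain, so the same applies.
- *Confirmed cases:* rest on histology.

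**4. The binomial statements in section 9.3**

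Inputs are 3,000 vaccinees, 1,000 placebo subjects, and rates of 1/1,000, 1/330 and 0.00005, all from section 9.3.

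- Chance of at least one event at 1/1,000: 1 − 0.999^3000 = 0.9503 (stated 95%).
- No case in 3,000, one-sided 95% upper limit: 1 − 0.05^(1/3000) = 0.000998, just below 1/1,000 as stated.
- At a true rate of 1/330: P(X ≤ 1) = 0.0011 and P(X ≤ 2) = 0.0057, both below 0.05 as stated.
- At 0.00005: P(X ≥ 1) = 13.93% and P(X ≥ 2) = 1.02% in 3,000; P(X ≥ 1) = 4.88% in 1,000 (stated 13.9%, 1.02%, 4.9%).

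All reproduce. They need complete ascertainment of cases in the stated number of subjects; none takes the number of ECGs or troponin tests as an input.

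**5. Sensitivity to missed cases**

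Let f be the share of true cases arising after dose 2 and d the share of those detected under indicated testing. The protocol gives neither, so both are assumptions. Overall ascertainment is s = 1 − f(1 − d), and the no-case limit becomes 0.998/s per 1,000.

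- f = 0.5, d = 0.9: s = 0.95, limit 0.998/0.95 = 1.05 per 1,000.
- f from 0.25 to 0.75, d from 0.5 to 0.9: s from 0.975 down to 0.625, limit 1.02 to 1.60 per 1,000.
- The below-1/330 conclusion holds at one-sided 0.05 for s of at least 0.52 with one case and at least 0.69 with two.

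**The case against.** The best defence is that the protocol never defines cardiac monitoring as ECG plus troponin. Section 8.2.7 opens with physical examination and auscultation, and everyone attending Visit 4 has these together with AESI recording. This part stands: monitoring after dose 2 is reduced, not absent. As a full answer it fits poorly. Auscultation is done at every visit from Visit 1 to Visit 5, so it would not single out the time points two weeks after each dose, and section 9.3 itself names ECG changes as something the all-subject monitoring will let one compare.

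A second defence is that the universal Visit 2 ECG in all four arms already provides a fair ECG comparison. It does, for dose 1. It does not reach the second administration, which section 9.3 includes by writing of each dose.

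Third, table layout belongs to the statistical analysis plan, which is not at hand. That is right, and missing table detail is not the point. The point is that the protocol misdescribes its own data collection, and an analysis plan cannot supply tests that are never scheduled.

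A reader might infer three stronger things that the documents do not support:

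- *That observing no case means something different after dose 1 and dose 2.* Possible and probable myo-/pericarditis require symptoms after either dose, and those symptoms prompt testing.
- *That the comparison with placebo is biased.* No passage says that Visit 2 and Visit 4 results will be pooled, and the indication rule is the same in all blinded arms. An equal rule does not guarantee equal testing if symptoms differ between arms, which is a reason not to rest an all-subject comparison on Visit 4; it does not show that bias will occur.
- *That the no-case conclusion fails because its limit, 0.998 against 1 per 1,000, has almost no slack.* The arithmetic is sensitive, as step 5 shows, but the protocol gives no detection share, and nothing in it indicates that symptomatic cases would be missed.

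**Conclusion.** The inconsistency is real. Section 9.3 claims cardiac monitoring of all subjects after each dose and ties it to ECG changes, while sections 1.6, 4.2.2, 8.2.7 and 8.2.8 provide universal ECG or troponin I only at screening and Visit 2. It affects one of the two post-dose time points, 4,000 of 8,000 as planned.

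The consequence is limited and specific: asymptomatic ECG- or troponin-defined AESIs after dose 2 are not systematically ascertained, and Visit 4 tests selected by symptoms cannot support an all-subject comparison with placebo. The myo-/pericarditis probability statements reproduce, do not rest on this sentence, and are largely unaffected, provided that subjects with cardiac symptoms after dose 2 report them and are tested as the protocol describes. No figure in section 9.3 needs recalculating on this account.

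**What to change.** Reconcile section 9.3 with sections 1.6, 4.2.2, 8.2.7 and 8.2.8. Which schedule applies is for the sponsor and its clinicians to decide. If the current schedule stands:

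- Correct the section 9.3 sentence to say which assessments every subject has after each dose: ECG and troponin I with examination after the first; examination, vital signs and event recording after the second, with ECG and troponin I only when indicated.
- State that the between-group comparison of ECG and troponin findings uses the scheduled Visit 2 results.
- Report Visit 4 and unscheduled ECG and troponin results separately, with the number of subjects tested in each arm as denominator.
- Note that asymptomatic ECG- and troponin-defined AESIs are not systematically ascertained after dose 2.

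The cost is a few lines of protocol text and a separate table for indicated tests. With the current schedule kept, no procedure is added, and the sample size and primary analysis do not change.
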